5.7.1. Analysis of Adverse Events

In general, the primary focus of AE reporting will be on TEAEs. Pre-treatment and post-treatment AEs will be provided separately.

If an AE date/time of onset (occurrence, worsening, or becoming serious) is incomplete, an imputation algorithm will be used to classify the AE as pre-treatment, treatment-emergent, or post-treatment. The algorithm for imputing date/time of onset will be conservative and will classify an AE as treatment-emergent unless there is definitive information to determine pre-treatment or post-treatment status. Details on classification of AEs with missing or partial onset dates are provided in Section 6.4.

Adverse event incidence tables will present the number (n) and percentage (%) of patients experiencing an AE by SOC, HLTG (when applicable), HLT (when applicable), and PT. Multiple occurrences of the same event in the same patient will be counted only once in the tables within a treatment phase. For tables presenting severity of events, the worst severity will be chosen for patients with multiple instances of the same event. The denominator for computation of percentages is the safety population within each treatment group.

The table of all TEAEs presented by SOC and PT will be sorted by the internationally agreed SOC order and decreasing frequency of PTs within SOCs (in the Praluent group). This will define the presentation order for all other tables by SOC and PT, unless otherwise specified. The tables of AEs by SOC, HLTG, HLT and PT will be sorted by the SOC internationally

agreed order and the other levels (HLGT, HLT, PT) will be presented in alphabetical order, unless otherwise specified.

Analysis of all treatment-emergent adverse events

The following TEAE summaries will be generated:

- Overview of TEAEs, summarizing number (%) of patients with any
 - TEAE;
 - Serious TEAE;
 - TEAE leading to death;
 - TEAE leading to permanent treatment discontinuation.
- All TEAEs by primary SOC, HLGt, HLT, and PT
- Number (%) of patients experiencing common TEAE(s) presented by primary SOC, HLT and PT (HLT incidence $\geq 5\%$ in any treatment group), sorted by SOC internationally agreed order and by alphabetic order for the other levels (HLT and PT);
- All TEAEs by primary SOC and PT, sorted by the internationally agreed SOC order and by decreasing incidence of PTs within each SOC (in the Praluent group).
- All TEAEs by treatment group regardless of relationship in one column and, in the same table a second column with TEAEs related to alirocumab according to investigator's opinion by primary SOC, HLGt, HLT and PT;
- All TEAEs by maximal severity (i.e., mild, moderate or severe), presented by primary SOC and PT, sorted as defined above;
- The event rate per patient-year (the number of patients with an event in question divided by total patient-years) will be provided for all TEAEs by SOC and PT. For a patient with event, patient year is censored at time of first event; for patient without event, it corresponds to length of TEAE period;
- Kaplan-Meier curves will be provided, when appropriate, for time from first dose of study treatment to the first occurrence of selected TEAEs as well as incidence rates at 24, 48, 72, and 96 weeks of exposure. Patients without any event will be censored at the end of the TEAE period. Selected TEAEs could be AESIs (e.g. neurocognitive events), or TEAE related to any clinically significant signal that needs further characterization;

- The frequency of selected AEs by SOC and PT over time during the treatment period (number of patients experiencing AE and percentage by patient-months) will be provided by time intervals defined as: ≤ 24 weeks, >24 to ≤ 48 weeks, >48 to ≤ 72 weeks, >72 to ≤ 96 weeks, using the PROC LIFETEST with the actuarial method. Only the first event will be counted.

Analysis of all treatment emergent serious adverse event(s)

- All serious TEAEs by primary SOC, HLT, HLT, and PT and by SOC/PT; Patient listings of serious TEAEs will be provided for the report appendix.
- All serious TEAEs by treatment group regardless of relationship in one column and in the same table a second column with TEAEs related to alirocumab according to investigator's opinion, by primary SOC, HLT, HLT, and PT;
- The event rate per patient-year will be provided for all serious TEAEs by SOC and PT.

Analysis of all treatment-emergent adverse event(s) leading to treatment discontinuation

- All TEAEs leading to permanent treatment discontinuation, by primary SOC, HLT, HLT, and PT and by SOC/PT; Patient listings of TEAEs leading to permanent treatment discontinuation will be provided for the report appendix.

Analysis of groupings of adverse events including selected adverse events of special interest

- All grouping of TEAEs including adverse events of special interest, as listed in Section 4.7.1.2, will be presented by SMQ/CMQ and PT (when selection is based on SMQs/CMQs) and by SOC and PT (when selection is based on the e-CRF tick box or HLT/HLT). The summaries will be sorted by decreasing incidence of PT within each SOC/SMQ (in the Praluent group).
- Neurocognitive events adjudicated by the neurocognitive events review committee will also be summarized by primary SOC and PT. They will also be summarized according to the adjudication of possible etiology of the neurocognitive events (Yes/No) (Section 4.7.1.2).
- All TEAEs within diabetes grouping will be analyzed overall and according to the diabetic status at baseline (i.e., in patients With and without diabetes at baseline).

The following variables will also be tabulated for the local injection site reactions TEAEs:

- Intensity of the event (mild, moderate, severe);
- Number of events divided by the number of study treatment injections received;

- Time from first study treatment injection to first injection site reaction;
- Description of the highest intensity of each symptom recorded in the specific e-CRF page with table and bar chart.

Description of symptoms and possible etiologies for General Allergic Reaction TEAE reported by investigator (using the tick box), will be presented.

Post-treatment adverse events

- All post-treatment AEs by primary SOC and PT, sorted by the internationally agreed SOC order and decreasing incidence of PTs (in the Praluent group) within each SOC;
- All post-treatment SAEs by primary SOC and PT, sorted by the sorting order defined above.

Subgroup of patients with two consecutive LDL-C <25 mg/dL (<0.65 mmol/L) and LDL-C <15 mg/dL (< 0.39 mmol/L)

If applicable, similar summaries of TEAEs as those described above will be provided on the safety subgroup population of patients with two consecutive results of LDL-C <25 mg/dL (as defined in Section 4.8) in both treatment groups. Only TEAEs for which it will be confirmed or unclear that they occurred, worsened or became serious on the day or after the day the first level of LDL-C <25 mg/dL was observed will be considered in this summary.

In addition, the neurocognitive event rate in patients with 2 consecutive results separated by at least 21 days, and with only 1 such event for calculated LDL-C <25 mg/dL, and calculated LDL-C <15 mg/dL, will be assessed.

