If any clinically significant signal is detected and further characterization is needed or for AEs of clinical interest, selected TEAEs will be analyzed using a time-to-event approach (Kaplan-Meier methodology) to account for the differential exposure time in all patients. Time from the first dose of study drug to the first occurrence of the event will be calculated (only the first event will be counted). Patients without any event will be censored at the end of the TEAE period. Kaplan-Meier curves will be provided.

Death

The following death summaries will be generated:

- Number (%) of patients who died by study period (TEAE and post-study) summarized on the safety population by treatment received
- Death in nonrandomized patients or randomized and not treated patients
- TEAE leading to death (death as an outcome on the AE e-CRF page as reported by the investigator) by (at least) SOCs sorted by internationally agreed order, and PTs sorted by decreasing frequency in the Praluent group, showing the number (n) and percentage (%) of patients

Drug-Induced Liver Injury

Liver function tests, namely ALT, AST, alkaline phosphatase, and total bilirubin, are used to assess possible drug-induced liver toxicity. The proportion of patients with potentially clinically significant abnormal values (PCSA) at any post-baseline visit by baseline status will be displayed by treatment group for each parameter. A graph of distribution of peak values of ALT versus peak values of total bilirubin will also be presented (note that the ALT and total bilirubin values are presented on a logarithmic scale). The graph will be divided into 4 quadrants with a vertical line corresponding to 3 x upper limit of normal (ULN) for ALT and a horizontal line corresponding to 2 x ULN for total bilirubin.

The incidence of liver-related AEs will be summarized by treatment group. The selection of PTs will be based on a standardized MedDRA query hepatic disorder. Time to liver-related treatment discontinuation and time to liver death may also be provided based on the hepatic disorder standardized MedDRA query.

Neurocognitive Events of Special Interest:

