3.1. Safety Analysis Sets

3.1.1. Safety Population

The safety population (SAF) will be defined as all patients randomized and exposed to at least 1 dose of study drug, regardless of the amount of treatment administered. Patients will be analyzed according to the treatment received (placebo or Praluent 75 mg Q2W/up-titrate 150 mg Q2W).

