4.7.1. Adverse Events Variables

The period of safety observation starts from the time when the patient gives informed consent and continues into the following periods:

- The PRE-TREATMENT period: defined as the time from the signed informed consent up to the first study treatment injection.
- The treatment-emergent adverse event (TEAE) period: defined as the time from the first study treatment injection up to the day of the last study treatment injection + 70 days (10 weeks), as residual effect of Praluent is expected until 10 weeks after last dose of study treatment.

The TEAE period will include:

- The TREATMENT period is defined as the time from the first study treatment injection up to the day of last study treatment injection + 21 days, as serum concentration of alirocumab >10 µg/mL is expected for approximately 21 days following administration of 150 mg. Further, in previous studies, alirocumab concentrations declining below this concentration also showed a decrease in effect on LDL-C.
- The RESIDUAL TREATMENT period is defined as the time from the day of last study treatment injection + 22 days up to the day of last study treatment injection + 70 days (10 weeks).
- The POST-TREATMENT period: defined as starting the day after the end of the TEAE periods (i.e., 71 days after the last study treatment injection) up to the patient's end of study.

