5.7.1.1. Patient Deaths

The following summaries of deaths will be generated.

- Number (%) of patients who died by study period (TEAE and post-treatment);
- Deaths in nonrandomized patients or randomized but not treated patients;
- TEAEs leading to death (death as an outcome on the AE CRF page, as reported by the Investigator) by (at least) SOC (sorted by internationally agreed order), and PT (sorted by decreasing frequency, showing the number (n) and percentage (%) of patients) for the safety population.

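### Post-treatment AE and SAE percentages, and deaths by period, are taken over the whole safety population, although a patient dosed to week 94 has no post-treatment time

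*SAP*

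**What the plan says.** SAP 5.7.1 states the denominator once for the AE incidence tables: "The denominator for computation of percentages is the safety population within each treatment group". Protocol 9.5.2.6 has the same rule. The safety population (SAP 3.1.1) is "all patients randomized and exposed to at least 1 dose of study drug, regardless of the amount of treatment administered".

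Under post-treatment adverse events, SAP 5.7.1 plans "All post-treatment AEs by primary SOC and PT, sorted by the internationally agreed SOC order and decreasing incidence of PTs", and a matching table for serious events. Neither has its own denominator. SAP 5.7.1.1 plans "Number (%) of patients who died by study period (TEAE and post-treatment"), again without one. The protocol's version of the death table is explicit: "Number (%) of patients who died by study period (TEAE and post-study) summarized on the safety population by treatment received".

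SAP 4.7.1 begins the post-treatment period on the day after the treatment-emergent (TEAE) period ends, "i.e., 71 days after the last study treatment injection) up to the patient's end of study". Protocol 9.5.2.6 closes it at the last study visit. The last dose is at week 94 and the last visit at week 96 (protocol 3.1 and Table 1).

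Event rates per patient-year are specified in SAP 5.7.1 for TEAEs and serious TEAEs, but not for post-treatment events.

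**The concern.** A percentage reads as a risk when everyone in the denominator could have had the event recorded. Here every on-schedule completer is in the denominator of the post-treatment tables without a single day in the period they describe. The printed figure is the product of two things: the risk among patients followed after washout, and the share of treated patients who stopped early enough and then stayed. No planned table shows the second factor.

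Two consequences follow. Within an arm, the percentage is lower than the incidence among patients actually followed. Between arms, a difference in early stopping or in retention can pass for a difference in risk, or hide one.

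**Working it through.** **Inputs.** Last dose at week 94; last visit on day 673 with a window of 7 days either side (protocol Table 1); TEAE period to last injection + 70 days (SAP 4.7.1); dropout of 20% in year 1 and 25% in year 2 (protocol 9.2, SAP 2.2).

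**1. The plan's own attrition figure.** With margin 0.2, SD 1.0, true difference 0, two-sided alpha 0.05 and 95% power, a two-sample noncentral t calculation gives 651 per arm (power 0.9501). Then 651 / (0.80 × 0.75) = 1085, which matches the plan. So the plan retains 60% and loses 40%. This is the only attrition assumption in the documents.

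**2. On-schedule completer.**
- Last dose: 1 + 94 × 7 = day 659.
- End of TEAE period: 659 + 70 = day 729; first possible post-treatment day: 730.
- Last visit: day 673, or day 680 at the end of its window.
- Shortfall: 729 − 673 = 56 days, or 729 − 680 = 49 days. Post-treatment time is zero, and this needs no assumption about dropout.

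**3. Who can contribute.** With the last visit on day 673, the last dose must fall on or before 673 − 71 = day 602 (week 85.86). The patient must also stay in the study. Protocol 7.3.1 asks those who stop drug to do so. Those who leave have a closing visit within 5 days of stopping treatment if possible (protocol 7.4.1), so they add almost nothing.

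**4. Size.** Factor = 1 / (share of the safety population with post-treatment time). Reading the planned dropout as drug discontinuation, with year 2 as weeks 52 to 96 and everyone who stops staying to week 96:
- Linear accrual: 0.20 + 0.80 × 0.25 × (85.86 − 52)/44 = 0.354; factor 1/0.354 = 2.8.
- Constant hazard: 1 − 0.80 × 0.75^(33.86/44) = 0.359; factor 1/0.359 = 2.8.
- If all 1085 per arm are dosed, that is about 384 to 389 patients per arm.

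**5. Other assumptions.**

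| Assumption | Observable share | Factor |
|---|---|---|
| 50% stop in time, all stay | 0.50 | 2.0 |
| All 40% stop in time, all stay | 0.40 | 2.5 |
| Year 2 taken as weeks 52 to 104, all stay | about 0.33 | 3.0 |
| 36% stop in time, half stay | 0.18 | 5.6 |

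If only a quarter of the 36% stay, the share is 0.09 and the factor about 11, so 5.6 is not a ceiling.

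**6. Between arms.** With equal true risk, the ratio of percentages equals the ratio of observable shares. Equal shares leave it at 1. A hypothetical 36% against 30% gives 0.36/0.30 = 1.2; the documents offer no evidence for such a gap.

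**The case against.** The share of all treated patients with a recorded post-treatment event is a legitimate descriptive quantity, and the plan does not claim to estimate risk per patient followed. SAP 5.7 rules out formal testing of safety data, and 5.7.1 puts the focus on TEAEs, which already have patient-year rates and Kaplan-Meier curves. Discontinuation and early termination are tabulated by arm (SAP 4.4 and 5.4), with Kaplan-Meier curves for stopping drug (5.5.1), so much of an imbalance would be visible. An at-risk denominator also depends on two events after randomization, stopping drug and staying in the study, so comparisons on it mix risk with selection. All of this stands. It argues against simply replacing the denominator. It does not argue against showing the at-risk number, which no planned table gives, or against labelling the percentage.

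Three stronger readings are tempting, and the documents do not support them:

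- A reader might take 2.8 as a minimum. It is one scenario. The 20% and 25% are a sample-size allowance, neither a discontinuation rate nor a bound on one. More stopping with good retention lowers the factor; poorer retention raises it.
- A reader might infer that these tables are the only view of what happens after washout. Hepatitis C seroconversion is also summarized over the period after the TEAE period (SAP 5.7.2), and antibody summaries take samples regardless of timing (SAP 5.9).
- A reader might treat deaths exactly like other events. Protocol 8.2 still takes fatal SAEs reported after the last visit, and 7.4.1 seeks vital status for patients who fail to return. The protocol's 'post-study' label could take in later deaths of completers, whereas the SAP's period ends at the patient's end of study.

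One small exception to the timeline: the week 96 analysis window runs to day 756 (SAP 10.2), so a visit delayed past day 729 would give a completer a few post-treatment days.

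**Conclusion.** The point holds as a reporting defect in descriptive tables. For AEs and SAEs it follows from the denominator rule and the calendar alone. For deaths by period the denominator is explicit in the protocol, but what is observable depends on which period label applies.

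The understatement is relative to incidence among patients followed after washout. The size of about 2.8 rests on reading planned dropout as drug discontinuation with full retention, and roughly 2.0 to 5.6 covers the other assumptions shown. Any distortion between arms depends on unequal observable shares. This is a cheap improvement, not a threat to the trial's main conclusions.

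**What to change.** In SAP 5.7.1 and 5.7.1.1:

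- Report by arm the number of safety-population patients with at least 1 day of observation after last injection + 70 days.
- Give post-treatment AEs, SAEs and deaths as a rate per patient-year of that observation, and as a percentage of that number. This follows the SAP's own practice: patient-year rates for TEAEs (5.7.1) and, for abnormal laboratory and vital-sign values, a denominator of patients assessed in the period (5.7).
- Label any percentage kept on the full safety population as a share of all treated patients.
- Align the protocol's 'post-study' and the SAP's 'post-treatment' labels for deaths, and close the count and the observation time at the same date.
- Record the change in SAP 1.2.3, now marked not applicable, because protocol 9.5.2.6 carries the same denominator rule.

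Keep the safety population as denominator for the TEAE tables.

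The cost is SAP wording and one derived flag with its observation time; no new data are needed. The downside is that the at-risk group is small and self-selected, so each table needs a note saying so.

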9.5.2.6. Adverse Events

All AEs reported in this study will be coded using the currently available version of the Medical Dictionary for Regulatory Activities (MedDRA®). The verbatim text, the preferred term (PT), and the system organ class (SOC) will be provided in patient listings.

Definitions

For safety variables, the following observation periods are defined:

- The pretreatment period is defined as the time from signing the ICF to before the first dose of study treatment.
- The TEAE period is defined as the time from the first dose of study treatment to the last dose of study treatment + 70 days (10 weeks) (residual effect of treatment is expected until 10 weeks after the last dose of study drug).
- The post-treatment observation period is defined as the time from the day after the end of the TEAE period up to the last study visit.

Pretreatment AEs are defined as those that developed, worsened, or became serious during the pretreatment period.

Treatment-emergent adverse events are defined as those that developed, worsened, or became serious during the TEAE period.

Post-treatment AEs are defined as those that developed, worsened, or became serious during the post-treatment period.

Analysis

Adverse event incidence tables will be presented by (at least) SOCs sorted by internationally agreed order, and PTs sorted by decreasing frequency in the Praluent group. The number (n) and percentage (%) of patients experiencing an AE will be shown. The high level group term and high level term can be added in alphabetical order, as applicable. Multiple occurrences of the same event in the same patient will be counted only once in the tables within a treatment phase. Data conventions for missing or partial AE dates will be addressed in the SAP. The denominator for computation of percentages is the safety population within each treatment group.

Adverse event incidence tables will be provided by treatment group for all types of TEAEs: all TEAEs, all TEAEs of interest (defined with a PT or a prespecified grouping), TEAE by severity, all treatment-emergent SAEs, and all TEAEs leading to permanent treatment discontinuation.

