1.2.2. Secondary and Exploratory Objectives

The secondary objectives are:

- To evaluate the effect of Praluent in comparison with placebo on lipoproteins
- To evaluate the safety and tolerability of Praluent

1.2.3. Modifications from the Statistical Section of Protocol Amendment 5

N/A.

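### Patient-year adverse event rates count up to 56 days after adverse event collection has ended, so rare non-serious rates come out about 7.7% too low in completers

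*SAP*

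**What the plan says.** SAP 5.7.1 (Analysis of Adverse Events) plans a rate per patient-year for all TEAEs by SOC and PT. The numerator is the number of patients with the event. In the denominator, a patient with the event contributes time to the first event; "for patient without event, it corresponds to length of TEAE period". The same section extends this to serious events: "The event rate per patient-year will be provided for all serious TEAEs by SOC and PT". For the Kaplan-Meier curves it uses the same end point: "Patients without any event will be censored at the end of the TEAE period". Protocol 9.5.2.6 states that censoring rule too.

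SAP 4.7.1 and protocol 9.5.2.6 both define the TEAE period as running from the first injection to 70 days after the last. Neither cuts it short at the last visit, last contact or death. SAP 6.4 uses the last-contact date only to impute a missing last-injection date.

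Collection follows a different clock. Protocol 7.6.4.4 records adverse events up to the last study visit, and protocol 8.2.5 up to the end of study visit, or the early termination visit if consent is withdrawn. The footnotes to protocol Table 1 put the last dose at week 94 and the last visit at week 96, and Table 1 schedules nothing later.

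Some reporting continues after the last visit. Under protocol 8.2, an SAE of which the investigator is informed is reportable if its onset is within 30 days of that visit; later ones only if fatal or judged drug-related. Protocol 8.2.1 requires deaths to be reported until 70 days after dosing.

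**The concern.** A rate is sound only if its denominator is time in which the numerator could have been recorded. Here the denominator for event-free patients includes weeks in which non-serious events are not collected. The error always runs in one direction: reported absolute rates are too low. Rates are planned for every preferred term, and for rare terms the shortfall is close to its maximum. Both documents call this a safety study (protocol 9.5.2.4, SAP 5.6.4), so absolute event rates are a main product.

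The protocol's own period definitions show the mismatch. Protocol 9.5.2.6 defines the post-treatment period as "the time from the day after the end of the TEAE period up to the last study visit". For a completer the TEAE period ends 728 days after first dose and the last visit is at 672 days, so this period would start after it ends.

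The concern is limited to patient-year rates and, to a small extent, Kaplan-Meier curves. Because the rule is identical in both arms, it does not claim a biased comparison.

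**Working it through.** The documents give no event rate or person-time total to reproduce. One input can be checked: week 96 is study day 96 × 7 + 1 = 673, which matches the target day in SAP Appendix 10.2, Table 2. Days below are counted from first dose.

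**Completer, rare non-serious event**
- Last dose (protocol Table 1, week 94): 94 × 7 = 658.
- Credited time (SAP 5.7.1 with 4.7.1): 658 + 70 = 728.
- Observed time (protocol 7.6.4.4; week 96 visit): 96 × 7 = 672.
- Gap: 728 − 672 = 56 days.
- Shortfall in the rate: 1 − 672/728 = **7.7%**. Equivalently, the matched rate is 728/672 = 1.083 times the planned one.

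**Permitted windows** (dosing ±3 days, protocol section 5; week 96 visit ±7 days, Table 1)
- Last dose 3 days early, visit 7 days late: 1 − 679/725 = 6.3%.
- Last dose 3 days late, visit 7 days early: 1 − 665/731 = 9.0%.

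**Less rare events in completers** (constant hazard h assumed). With observed time O, credited time T and p = 1 − exp(−hO), observed person-time is p/h and credited person-time is p/h + (1 − p)(T − O). The shortfall is 7.7% at a 96-week incidence of 1%, 7.3% at 10% and 5.5% at 50%.

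**Serious events in completers.** If the 30-day reporting rule is treated as full observation, observed time is 672 + 30 = 702 and the shortfall is 1 − 702/728 = 3.6%.

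**Whole arm.** This needs assumptions. Read the planned dropout of 20%, then 25% of the remaining 80% (another 20%), as stopping drug, which leaves 60% completers. Take last dose as uniform over weeks 0–52 (mean 182 days) and weeks 52–94 (mean 511 days).
- Mean credited time: 0.6 × 728 + 0.2 × (182 + 70) + 0.2 × (511 + 70) = 603.4 days.
- All stoppers stay in the study, as protocol 7.3.1 asks. Only last doses after day 602 leave a gap, averaging 56²/(2 × 294) = 5.3 days among second-year stoppers. Unobserved: 0.6 × 56 + 0.2 × 5.3 = 34.7 days; 34.7/603.4 = 5.7%.
- All leave, last visit 19 days after last dose (one missed 14-day dose + 5), gap 51: (0.6 × 56 + 0.4 × 51)/603.4 = 54.0/603.4 = 8.9%.
- All leave, last visit 5 days after last dose (the target in protocol 7.4.1), gap 65: (33.6 + 26.0)/603.4 = 59.6/603.4 = 9.9% in the rare limit.

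| Event type | All stay | All leave, 19 days | All leave, 5 days |
|---|---|---|---|
| Non-serious, 0.01 per patient-year | 5.7% | 8.9% | 9.8% |
| Serious, 0.01 per patient-year, 30-day reporting as observation | 2.6% | 4.0% | 4.9% |
| Non-serious, 1.5 per patient-year | 1.0% | 3.9% | 4.9% |

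**Kaplan-Meier at week 96** (hazard 0.1 per patient-year assumed). The true value is 1 − exp(−0.1 × 672/365.25) = 0.168. The planned censoring gives 0.168 if all stoppers stay, and 0.163 (19 days) or 0.161 (5 days) only if all leave.

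**The case against.** The strongest points on the other side are these.

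- **No completer-only rate is planned.** The reported figure is for a whole arm, and its error depends on assumed dropout timing and on how many stoppers stay. This stands: 7.7% is exact for an on-schedule completer, while 6% to 10% is conditional.
- **The window range is not the widest the documents allow.** Protocol section 5 lets a delayed injection be given up to 7 days late: 1 − 665/735 = 9.5%. SAP 4.4 counts 94 weeks of exposure as complete, which a last dose at week 92 satisfies (644 + 70 = 714): 1 − 672/714 = 5.9%, or 1 − 679/714 = 4.9% with a late visit. This also stands, but it adds scenarios and does not alter the mechanism.
- **The cap may be implied.** SAP 4.7.1 presents the TEAE period as part of the period of safety observation, so it might be read as ending when observation ends. This does not hold against an explicit 70-day definition; a programmer following the text would credit the full period.
- **The Kaplan-Meier change is close to a preference.** Agreed: its effect is negligible, and it is proposed only for consistency.
- **An onset filter has a cost.** Numerators in the rate tables will no longer match the n (%) tables, and some post-visit serious events, including fatal ones, drop out of the rate. True, and it should be footnoted.
- **The rates are descriptive and both arms are treated alike.** True, and this limits the importance. A descriptive rate still needs matching numerator and denominator.

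**Conclusion.** The concern holds. Applied as written, SAP 5.7.1 gives absolute patient-year rates that are too low, because event-free patients contribute time after routine adverse event collection has ended. In on-schedule completers the shortfall for rare non-serious events is 7.7% (6.3% to 9.0% over the stated dosing and visit windows), using only figures in the documents. For serious events in completers it is 3.6%, if the 30-day reporting is taken as full observation.

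Whole-arm figures of about 6% to 10% (rare non-serious), 1% to 5% (common, 1.5 per patient-year) and 2.6% to 4.9% (serious) rest on the assumed dropout timing, a constant hazard and the share of stoppers who remain in the study. If most stay, the low end applies.

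The mechanism is certain and the size is modest. It does not threaten the primary conclusion, but it should be corrected before database lock.

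**What to change.** In SAP 5.7.1, for patient-year rates:

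1. End at-risk time at the earliest of last dose + 70 days, the date adverse event collection ended (last study or early termination visit) and death. Count only events with onset on or before that date.
2. For serious TEAE rates, state one cut that applies to both numerator and denominator: either the date in item 1, or last visit + 30 days, capped at last dose + 70 days and at death. Capping time alone while still counting serious events after the visit would overstate the rate, by 702/672 − 1 = 4.5% in completers.
3. Use the item 1 date to censor the Kaplan-Meier curves, for consistency. Protocol 9.5.2.6 states the present censoring rule, so record the departure in SAP 1.2.3 ("Modifications from the Statistical Section of Protocol Amendment 5"), which now reads N/A.

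Leave the TEAE classification, death summaries and crude n (%) tables as they are.

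The cost is a short SAP paragraph, the entry in 1.2.3, one derived end-of-observation date and one onset filter in the code. No new data or visits are needed. Reported rates will rise slightly. A few serious events after the last visit, some possibly fatal, will appear only in the crude tables; under the 30-day option, only those with onset more than 30 days after that visit. A footnote to the rate tables should say so.
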